5.2 Exclusion Criteria

Participants are excluded from the study if any of the following criteria apply:

Medical Conditions

- 1 As judged by the investigator, any evidence of a condition, which in the investigator's opinion, makes it undesirable for the participant to participate in the study.
- 2 eGFR < 40 mL/min/1.73m² using the CKD-EPI.
- 3 History or presence of gastrointestinal, hepatic or renal disease or any other conditions known to interfere with absorption, distribution, metabolism or excretion of drugs, per the investigator's judgement.
- 4 Any uncontrolled or serious disease, or any medical (eg, known major active infection or major haematological, renal, metabolic, gastrointestinal or endocrine dysfunction) or surgical condition that, in the opinion of the investigator, may either interfere with participation in the clinical study and/or put the participant at significant risk (according to the investigator's judgment) if he/she participates in the clinical study.
- 5 Poorly controlled T2DM, defined as HbA1c > 10%.
- 6 Acute ischaemic cardiovascular event, including stroke, within 30 days, or heart failure with New York Heart Association (NYHA) Class III to IV.
- 7 Blood dyscrasias with increased risk of bleeding including idiopathic thrombocytopenic purpura and thrombotic thrombocytopenic purpura or symptoms of increased risk of bleeding (frequent bleeding gums or nose bleeds).
- 8 High-risk of bleeding diathesis or any anti-platelet therapy other than low dose aspirin (\leq 100 mg/day).
- 9 Malignancy (except non-melanoma skin cancers, cervical in situ carcinoma, breast ductal carcinoma in situ, or Stage 1 prostate carcinoma) within the last 10 years.
- 10 Recipient of any major organ transplant, eg, lung, liver, heart, bone marrow, renal.
- 11 LDL or plasma apheresis within 12 months prior to randomisation.

- 12 Uncontrolled hypertension defined as average sitting SBP > 160 mmHg or DBP > 90 mmHg.
- 13 Heart rate after 10 minutes sitting rest < 50 or > 100 bpm.
- 14 Any laboratory values with the following deviations at the Screening Visit; test may be repeated at the discretion of the investigator if abnormal:
 - Any positive result on screening for serum hepatitis B surface antigen, hepatitis C antibody, and human immunodeficiency virus (HIV)
 - ALT > 1.5 × ULN
 - AST > 1.5 × ULN
 - TBL > ULN
 - ALP > 1.5 × ULN
 - WBC < lower limit of normal (LLN).
 - Haemoglobin < 12 g/dL in males or < 11 g/dL in females
 - Platelet count ≤ LLN

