8.2.3 Assessments for AEs, including new onset/worsening of diabetes AEs

An assessment of AEs will be performed at the time points specified in the SoA. These AEs will also include any worsening of previously documented medical conditions as determined by the investigator.

Additionally, assessments for hyperglycemia-related AEs should be included with the

assessment for concomitant medications and AEs. This should include:

Any report of ‘New onset of diabetes’ in which participants with no medical history of diabetes are found to have any of the following:

- a post-baseline HbA1C $\geq 6.5\%$, confirmed by a consecutive HbA1C value $\geq 6.5\%$ (48 mmol/mol) or a fasting plasma glucose ≥ 126 mg/dL (7.0 mmol/L), **or**
- two consecutive values of fasting plasma glucose ≥ 126 mg/dL (7.0 mmol/L), **or**
- addition of a new concomitant medication for control of plasma glucose (if additional information provided to the investigator supports the diagnosis), **or**
- adverse events suggestive of diabetes (e.g. typical diabetes manifestations, signs, symptoms, complications).

Any report of ‘Worsening of the glycemic control’ or ‘diabetic complications’ in which participants with a medical history of diabetes are found to have:

- Absolute increase in HbA1c from baseline of $> 0.5\%$ (5.5 mmol/mol), and/or
- A new concomitant antidiabetic medication or an increase in dose of current antidiabetic therapy in response to uncontrolled diabetes, or any confirmation of uncontrolled diabetes/worsening glycemic control from clinical data collected by the investigator

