8.3.5 Adverse Events Based on Examinations and Tests

The results from the CSP mandated laboratory tests and vital signs will be summarised in the CSR.

Deterioration as compared to baseline in protocol-mandated laboratory values and vital signs should therefore only be reported as AEs if they fulfil any of the SAE criteria, are the reason for discontinuation of treatment with the investigational product or are considered to be clinically relevant as judged by the investigator (which may include but not limited to consideration as to whether treatment or non-planned visits were required or other action was taken with the study intervention, eg, dose adjustment or drug interruption).

If deterioration in a laboratory value/vital sign is associated with clinical signs and symptoms, the sign or symptom will be reported as an AE and the associated laboratory result/vital sign will be considered as additional information. Wherever possible the reporting investigator uses the clinical, rather than the laboratory term (eg, anaemia versus low haemoglobin value). In the absence of clinical signs or symptoms, clinically relevant deteriorations in non-mandated parameters should be reported as AE(s).

Any finding from physical examination (including neurological examination) should be evaluated as normal/abnormal. If the abnormal physical finding (including neurological examination) started prior to enrolment, it must be recorded as medical history. If the abnormal physical finding (including neurological examination) started or worsened after

enrolment, it must be recorded as an Adverse Event.

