9.4.1 General Considerations

Handling of multiple methods for measuring LDL-C

The LDL-C value obtained using PUC will be used in the analysis of LDL-C through reflex testing when the LDL-C is < 40 mg/dL (by the Friedewald method) or if the triglycerides are ≥400 mg/dL. If there is no measurement taken using PUC, the calculated LDL-C value obtained using the Friedewald formula will be used (CCI [REDACTED]). If neither LDL-C measured with PUC or calculated using the Friedewald formula is available, the measurement will be considered as missing. Further details or any additional measurement methods will be described in the SAP.

Baseline

For analyses based on the SAS, the baseline value is defined as the last non-missing value prior to or on the date of administration of the first dose of IMP. For analyses based on the FAS, the baseline value is defined as the last non-missing value prior to or on the date of randomisation. Details are described in the SAP.

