9.4.3.1 Primary Endpoint(s)

Adverse Events

Safety variables will be summarised by treatment group and visit using descriptive statistics (n, mean, SD, median, minimum and maximum [and geometric mean and coefficient of variation, if applicable]) for continuous data and absolute and relative frequencies for categorical data.

Clinical laboratory data and ECG parameters will be summarised by treatment group and visit.

Adverse events will be summarised by PT and SOC using MedDRA vocabulary. Adverse events that led to discontinuation of IMP, SAEs, AEs by severity and causally related AEs will also be presented. All AE summaries will be done by treatment group. Adverse events will be coded using the most recent version of MedDRA that will have been released for execution at AZ.

AEs will be presented for each treatment group by SOC, PT covering number and percentage of participants reporting at least one event and number of events where appropriate.

An overview of AEs will present for each treatment group the number and percentage of participants with any AE, AEs with outcome of death, serious AEs, and AEs leading to discontinuation of IMP, as well as AEs leading to IMP interruptions.

AEs of ISRs will be summarised separately.

Separate AE tables will be provided taking into consideration relationship to IMP as assessed by the investigator, seriousness, death and events leading to discontinuation of IMP and other significant adverse events and timing of events.

An additional table will present number and percentage of participants with most common AEs. Most common (eg, frequency \geq x%) will be defined in the SAP.

In accordance with the requirements of the FDA, a separate table will present non-serious AEs occurring in more than 5% of participants in any treatment group.

Key participant information will be presented for participants with AEs with outcome of death, serious AEs, and AEs leading to discontinuation of IMP.

An AE listing for the safety analysis set will cover details for each individual AE; an AE listing for participants who were not exposed to IMP is presented separately.

Full details of AE analyses will be provided in the SAP.

AEs occurring prior to start of IMP and treatment emergent AEs will be presented separately.

Treatment emergent

The following events are considered treatment emergent:

- Adverse events with an onset date on or after first dose of IMP
- Worsening of pre-existing events on or after first dose of IMP

Vital signs

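### Section 8.2.3 puts no baseline condition on new-onset diabetes, so diabetes present but unrecorded at randomisation can be reported as a new on-study event

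*Protocol*

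**What the plan says.** Section 8.2.3 sets two categories of hyperglycaemia-related adverse event.

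- **New onset.** The only population condition is the absence of a recorded history: "participants with no medical history of diabetes are found to have any of the following". The HbA1c criterion is "a post-baseline HbA1C $\geq 6.5\%$, confirmed by a consecutive HbA1C value" at or above the same threshold, or by a fasting glucose of at least 126 mg/dL. The glucose criterion is "two consecutive values of fasting plasma glucose" of at least 126 mg/dL, without the post-baseline limit that the HbA1c criterion carries. A new glucose-lowering drug or adverse events suggestive of diabetes also qualify.
- **Worsening.** This applies only to participants with a history of diabetes. Its HbA1c criterion is tied to baseline: "Absolute increase in HbA1c from baseline of" more than 0.5%.

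Other sections that bear on the point:

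- Section 5.2, criterion 5, excludes "Poorly controlled T2DM, defined as HbA1c > 10" per cent. No other eligibility criterion sets a limit on HbA1c or glucose.
- The Schedule of Activities has HbA1c at screening, randomisation, Visit 16 and Visit 18. Glucose is taken at randomisation, the dosing visits, Visit 16 and Visit 18. Section 5.3.1 makes all of these fasting visits. Medical history is scheduled at Visit 1 only.
- Section 8.3.5 says "Deterioration as compared to baseline in protocol-mandated laboratory values and vital signs should therefore only be reported as AEs if" they are serious, lead to stopping the product, or are judged clinically relevant.
- Section 9.4.1 already defines a safety baseline: "For analyses based on the SAS, the baseline value is defined as the last non-missing value prior to or on the date of" first dosing.
- Section 9.4.3.1 classes as treatment emergent "Adverse events with an onset date on or after first dose of IMP", as well as worsening of pre-existing events.

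**The concern.** A definition of new onset should separate disease that began on study from disease that was already there. This one separates participants by whether somebody had diagnosed them before entry. Baseline HbA1c and glucose are measured but play no part in deciding who can become a new-onset case.

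Safety is a primary objective, and Section 2.1 describes the aim as a safety database able to show signals that might restrict the treated population. If prevalent cases enter the new-onset count, the incidence is overstated in both arms, and a relative comparison looks weaker than it is. The definition also governs what sites report, so sites that handle it differently will produce uneven data.

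**Working it through.** **1. Can an unchanged participant meet the definition?** Take two participants whose HbA1c is 6.8% at screening, Visit 2, Visit 16 and Visit 18.

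| | History of diabetes recorded | No history recorded |
|---|---|---|
| Rule that applies | Worsening | New onset |
| HbA1c test | Rise above 0.5% | Post-baseline value at least 6.5%, confirmed |
| Values | 6.8 − 6.8 = 0 | 6.8 at Visit 16, 6.8 at Visit 18 |
| Result | No event | New-onset event |

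Neither participant changed. For glucose, a value of at least 126 mg/dL before dosing at Visit 2 and another at Visit 4 are consecutive fasting values, so a baseline sample can supply half of the pair.

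**2. Does another section prevent this?**

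- Eligibility: an undiagnosed participant with HbA1c from 6.5% to 10% is not excluded on that ground.
- Medical history: no rule requires a diabetic-range screening value to be entered as history. The rule in Section 8.3.5 that turns earlier abnormalities into history covers physical and neurological findings only.
- Laboratory adverse events: Section 8.3.5 presumes deterioration from baseline, and an unchanged 6.8% is none. Section 8.2.3 does not refer to it, and as the more specific rule it points the other way.
- Treatment emergence: this works by onset date. A case first recognised at Visit 16 can carry a post-dose date.

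None of these reliably closes the gap.

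**3. How large could the effect be?** The protocol gives no diabetes rate, so there is no figure of its own to reproduce. From Section 9.2: 376 randomised 1:1, hence 376 / 2 = 188 per arm. Assumed, not from the documents: u, the share with undiagnosed diabetes at baseline, 1% to 5%; true incident risks of 2% on placebo and 4% or 6% on active.

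Misclassified cases per arm = 188 × u. Observed risk = u + (1 − u) × p. This is an upper bound, because it lets every prevalent case go unrecorded and then meet a criterion.

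| u | Misclassified per arm | Observed ratio, true 2.0 (2% v 4%) | Observed ratio, true 3.0 (2% v 6%) | Observed difference, true 4.00 points (2% v 6%) |
|---|---|---|---|---|
| 1% | 1.9 | 1.66 | 2.33 | 3.96 |
| 2% | 3.8 | 1.49 | 1.99 | 3.92 |
| 3% | 5.6 | 1.39 | 1.79 | 3.88 |
| 5% | 9.4 | 1.28 | 1.55 | 3.80 |

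Example at u = 2%, 2% v 4%: (0.02 + 0.98 × 0.04) / (0.02 + 0.98 × 0.02) = 0.0592 / 0.0396 = 1.49.

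The u terms cancel in the difference, which becomes (1 − u) times the true value and so shrinks by only 1% to 5%. Excluding baseline cases restores the true ratio.

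**The case against.** The strongest reply is that Section 8.2.3 instructs sites on what to report and does not define an endpoint. Section 9.4.3.1 names separate summaries for injection site reactions and thrombocytopenia-related events but none for diabetes, and Section 9.4.3 makes safety descriptive unless otherwise specified. It leaves full detail of the adverse event analyses to the SAP, where a baseline flag could be derived. This stands as far as analysis goes: a reader might infer that a planned comparison is biased or that a test loses power, and the protocol shows no such comparison or test. It does not rescue the definition, because the reporting rule is fixed in the protocol and a later flag cannot fully undo uneven reporting.

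Sites can also see the problem coming. Visit 1 laboratory results must be reviewed before Visit 2, the blinding in Section 6.3 concerns the lipid panel rather than HbA1c, and an investigator may enter a diabetic-range screening value as history. That would move the participant to the worsening rule. The protocol permits this but does not ask for it, so prevalent cases can count rather than always do. A glucose pair that starts at the pre-dose Visit 2 sample may likewise be given a pre-dose onset, though nothing settles it.

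Finally, the summary of changes says the criteria follow an FDA recommendation. That recommendation is not available here, so whether the omission was intended cannot be judged. Intended or not, it leaves Sections 8.2.3 and 8.3.5 at odds.

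**Conclusion.** The point holds as a defect in a reporting definition. Diabetes present but unrecorded at randomisation can be reported as new onset without any change, and Section 8.2.3 conflicts with the premise of Section 8.3.5.

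The consequence is an overstated new-onset count in both arms and a risk ratio drawn towards 1. At an assumed undiagnosed prevalence of 1% to 5%, at most about 2 to 9 participants per arm of 188 are affected, and a true ratio of 2.0 could appear as 1.66 down to 1.28. These sizes rest on prevalence and incidence figures that the documents do not give.

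A reader might go further and infer that the rule favours one arm or hides a signal on every scale. That is not supported. Randomisation balances prevalent cases in expectation, the risk difference shrinks by 1% to 5% at most under these assumptions, and no formal error rate is touched. The correction is worth making because it is cheap and safety is a primary objective.

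**What to change.** In Section 8.2.3:

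1. Limit new onset to participants with no history of diabetes whose baseline HbA1c is below 6.5% and baseline fasting glucose below 126 mg/dL, using the baseline in Section 9.4.1. This covers all four criteria, including the medication and symptom ones.
2. Require every qualifying HbA1c and glucose value, including the confirming one, to be post-baseline.
3. Report participants with no history but diabetic-range baseline values separately, or assess them under the existing baseline-anchored worsening criterion.
4. Reconcile Section 8.2.3 with Section 8.3.5, with a cross-reference that says which governs glycaemic values.

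The cost is a sentence or two of protocol text and one derived flag. Both baseline measurements are already scheduled, the thresholds are the protocol's own, and no visit or sample is added.

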8.2.4 Vital Signs

Vital signs (blood pressure, pulse and temperature) will be performed at the time points specified in the SoA.

- Blood pressure and pulse measurements will be assessed in a sitting position with a completely automated device. Manual techniques will be used only if an automated device is not available
- BP and pulse measurements should be preceded by at least 5 minutes of rest for the participant in a quiet setting without distractions (eg, television, cell phones)

Vital signs (to be taken before blood collection for laboratory tests) will consist of 1 pulse and 3 BP measurements (3 consecutive BP readings will be recorded at intervals of at least 1 minute). The average of the 3 BP readings will be recorded on the eCRF.

8.2.5 Electrocardiograms

ECG will be performed pre-dose where applicable, at timepoints specified in the SoA.

- At randomisation (Visit 2), the baseline 12-lead ECG will be obtained on three consecutive occasions after the participant has rested in supine position for at least 10 minutes

- During the treatment period and safety follow-up, a single 12-lead ECG will be obtained after the participant has rested in supine position for at least 10 minutes
- The same recorder should be used for each participant at each time point, if possible

The investigator (or qualified designee) will make an overall evaluation of the ECG as normal or abnormal. If abnormal, it will be decided whether the abnormality is clinically significant or not clinically significant, and the reason for the clinically significant abnormality will be recorded on the eCRF.

Abnormal values shall not be recorded as AEs unless deemed clinically significant. The printout of the ECG is to be signed, dated, and filed in the investigative site file along with a signed and dated copy (if the printouts are not on archive-quality paper).

The investigator may perform additional 12-lead ECG assessments in case of any abnormal findings or if considered required by the investigator for any other safety reason. These assessments should be entered as an unscheduled assessment.

8.2.6 Clinical Safety Laboratory Assessments

Laboratory variables will be analysed at Labcorp central laboratory. Any local laboratory variables, performed for safety assessment, such as platelet count, must be confirmed by central laboratory assessment. Samples will be collected, handled, labelled, stored and shipped as detailed in the laboratory manual.

The following laboratory variables will be measured.

Table 5 Laboratory Safety Variables

Haematology/Haemostasis (whole blood)	Clinical Chemistry (serum or plasma)
White blood cell (WBC) count	Sodium
Red blood cell (RBC) count	Potassium
Haemoglobin (Hb)	Blood urea nitrogen (BUN)
Haematocrit (HCT)	Creatinine
Mean-corpuscular volume (MCV)	Calcium
Mean corpuscular haemoglobin concentration (MCHC)	Phosphate
Neutrophils absolute count	Creatine kinase (CK)
Lymphocytes absolute count	Direct bilirubin
Monocytes absolute count	Alkaline phosphatase (ALP)
Eosinophils absolute count	Alanine aminotransferase (ALT)
Basophils absolute count	Aspartate aminotransferase (AST)
Platelets absolute count	Gamma glutamyl transpeptidase (GGT)
Reticulocytes absolute count	Total bilirubin (TBL)

Table 5 Laboratory Safety Variables

	Glutamate dehydrogenase (GLDH)
Urinalysis (dipstick)	Bicarbonate
Urinalysis (positive dipstick)	Uric acid
pH	Follicle stimulating hormone (FSH[women only])
Specific gravity	Luteinising hormone (LH) (women only)
Glucose	Haemoglobine A1c, glycated haemoglobin (HbA1c)
Blood	Glucose
Colour	Estimated glomerular filtration rate (eGFR) by CKD-EPI formula)
Protein	
Clarity/Appearance	Coagulation
Nitrites	Prothrombin time
Ketones	Activated partial thromboplastin time (aPTT)
Leukocytes	International normalised ratio (INR)
Microscopic analysis (if positive for blood, nitrites or protein)	
Urobilinogen	Urine renal safety biomarkers
	Albumin
	Total protein
Other Laboratory Assessments	Creatinine
Complement activation panel (Bb, C5a)	Urine protein to creatinine ratio (UPCR)
High-sensitivity C-reactive protein (hs-CRP)	Urine albumin to creatinine ratio (UACR)

NB. If a participant shows an AST **or** ALT $\geq 3 \times$ ULN **together with** TBL $\geq 2 \times$ ULN please refer to [Appendix E](#). Actions required in cases of increases in liver biochemistry and evaluation of Hy's Law, for further instructions.

8.3 Adverse Events and Serious Adverse Events

The PI is responsible for ensuring that all staff involved in the study are familiar with the content of this section.

The definitions of an AE or SAE can be found in [Appendix B](#).

Adverse events will be reported by the participant (or, when appropriate, by a caregiver, surrogate, or the participant's legally authorised representative).

The investigator and any designees are responsible for detecting, documenting, and recording events that meet the definition of an AE. Care will be taken not to introduce bias when detecting AEs and/or SAEs. Open-ended and non-leading verbal questioning of the participant is the preferred method for determining the occurrence of AEs.

8.3.1 Time Period and Frequency for Collecting AE and SAE Information

AEs will be collected from randomisation, (Visit 2) and SAEs from signing the ICF (Visit 1). Both AEs and SAEs will continue to be collected throughout the treatment period and including the follow-up period (Visit 18).

If the investigator becomes aware of an serious adverse event with a suspected causal relationship to the IMP that occurs after the end of the clinical study in a participant treated by him or her, the investigator shall, without undue delay, report the SAE to the sponsor.

8.3.2 Follow-up of AEs and SAEs

Any AEs that are unresolved at the participant's last AE assessment in the study are followed up by the investigator for as long as medically indicated, but without further recording in the eCRF. AstraZeneca retains the right to request additional information for any participant with ongoing AE(s)/SAE(s) at the end of the study, if judged necessary.

Adverse event variables

The following variables will be collected for each AE:

- AE (verbatim)
- The date when the AE started and stopped
- Maximum intensity (mild, moderate, severe)
- Whether the AE is serious or not
- Whether the AE required treatment
- Whether the AE was assessed as an ISR
- Investigator causality rating against the IMP(s) (yes or no)
- Action taken with regard to IMP(s)
- Outcome

In addition, the following variables will be collected for SAEs:

- Date AE met criteria for SAE
- Date investigator became aware of SAE
- AE is serious due to
- Date of hospitalisation
- Date of discharge
- Probable cause of death if applicable
- Date of death
- Autopsy performed
- Causality assessment in relation to study procedure(s)
- Causality assessment in relation to other medication

